2 PROTOCOL SYNOPSIS

TITLE: A Randomized, Double-Blind, Placebo-Controlled, Parallel-Group, Phase 2 Study to Evaluate the Safety and Efficacy of CT1812 in Subjects with Mild to Moderate Alzheimer's Disease.

SPONSOR: Cognition Therapeutics Inc.

PROTOCOL NUMBER: COG0201

CLINICAL STUDY PHASE: Phase 2

STUDY DRUG PRODUCT: CT1812

STUDY OBJECTIVES:

Primary:

 To assess the safety and tolerability of CT1812 as a treatment for mild to moderate Alzheimer's disease.

Secondary:

 To assess target engagement and identify pharmacodynamic effects of CT1812 on CSF biomarkers.

Exploratory:

- To characterize the PK profile of CT1812 in plasma.
- To assess the efficacy of CT1812 as a treatment for mild to moderate Alzheimer's disease.

STUDY DESIGN:

This is a multi-center, randomized, double-blind, placebo-controlled, parallel group 36 week multicenter Phase 2 study of two doses of CT1812 in adults with mild to moderate Alzheimer's Disease (AD).

Participants will be screened for eligibility by physical, laboratory, psychometric and neurologic examinations, and neuroimaging. Pre-drug CSF and blood samples will be obtained \leq 42 days prior to randomization at Baseline/Day 1. After having met all inclusion

criteria, and none of the exclusion criteria, participants will be randomized to one of three treatment arms (CT1812 at doses of 100 or 300 mg/d or placebo, up to n=48 group). Participant

Participants will be enrolled in three parts of the study, referred to as Part A, Part B and Part C. Part A is defined as the first 24 participants enrolled in the trial, and an interim analysis will be conducted on these participants. Part B is defined as the 25th participant through the 62nd participant enrolled in the trial. Part C is defined as all participants enrolled after October 2021.

Participants in Part A and B will return to the clinic twice in the first week after baseline, weekly for three weeks, bimonthly until Day 70, then every four weeks until Day 182 (See Table 1). A follow up visit will occur approximately 30 days after the end of treatment.

Participants in Part C will return to the clinic on Day 7 and Day 14 after baseline, followed by twice-monthly visits until Day 70, then every four weeks until Day 182 (See Table 1). A follow up visit will occur approximately 30 days after the end of treatment.

Participants who prematurely discontinue the study for any reason will be asked to attend a final safety and efficacy visit. Additional participants may be added to replace participants with significant disruption to their visit schedule due to COVID or if there are unanticipated dropouts.

Following an adequate clinical and non-clinical safety review of data from this initial cohort of participants, the protocol may be amended to expand enrollment and treatment duration to 12 months.

The study start date is defined as the date on which the first Informed Consent is signed. A participant is considered to have completed the study if he/she has completed all study visits. The end of the study is defined as the date of the last visit or the date of the last procedure of the last participant in the study.

Safety Stopping Rules:

Dosing may be terminated by the Sponsor at the recommendation of the DSMB (Data Safety and Monitoring Board) based upon safety and tolerability data, or at the discretion of the Sponsor; therefore, there are no study-specific stopping rules defined in this protocol.

The occurrence of any one of the following events will result in a review of study safety information to date by the Sponsor and DSMB.

- Two occurrences of the same or similar serious adverse event (SAE) assessed as
 probably or possibly related to dosing with investigational product.
- Two or more different participants with the same or similar severe AE assessed as
 probably or possibly related to the investigational product.
- Four or more participants with the same or similar moderate AE which is possibly or probably related to dosing with investigational product.

The Sponsor and DSMB will review the available safety data and recommend whether dosing should continue, study drug administration should be terminated, or additional monitoring procedures or safety precautions need to be employed. Selective unblinding of participants in the study may be performed by the DSMB to determine if the SAEs/AEs are isolated to a single dose group or if they occurred in placebo participants.

The study or a dose group may also be terminated if the DSMB determines that any adverse event(s) are occurring that are intolerable or pose a medically unacceptable safety risk.

In the case of an emergency, the Principal Investigator may unblind a participant without the Sponsor's approval, however, the Sponsor should be notified if a participant is unblinded as soon as possible.

For individual participants:

Any participant who develops the following liver function test (LFT) laboratory abnormalities will not receive any additional doses of study drug and will be monitored until the return of laboratory abnormality to the acceptable screening value(s).

- Elevated ALT or AST greater than 5 X Upper Limits of Normal (ULN)
- Elevated ALT or AST greater than 3 X ULN in combination with total bilirubin > 2
 X ULN or INR > 1.5 X ULN
- Elevated ALT or AST > 3 X ULN with the appearance of fatigue, nausea, vomiting, right upper quadrant pain or tenderness, fever, rash, and/or eosinophilia (>5%)

Serial monitoring of ALT/AST/bilirubin and INR will be performed, initially with repeat values within 4 days of discontinuation of study drug. If LFTs are still elevated 4 days post-study drug interruption, participants should have LFTs checked again 4 days later (+/- 1 day). The site investigator and Medical Monitor should agree to a plan for further LFT

monitoring depending on whether the LFTs are still increasing or trending towards normal. Repeat testing should be carried out until LFTs have normalized. The LFTs in this instance can also be run locally for more rapid turnaround.

In the event a reversible etiology is found to explain the elevated liver enzymes (such as a common bile duct stone), drug may be restarted following normalization of LFTs, and after discussion between the Medical Monitor and site PI. If an alternative etiology is not identified, dosing of the study drug will be permanently discontinued, and the participant will be withdrawn from the study.

Study drug will be temporarily discontinued if a participant does not achieve the aforementioned levels of elevated transaminases but has an elevation of ALT or AST >3 X ULN. These participants will have their liver function retested within 4 days after their last dose of study drug. If transaminases are still elevated 4 days post-study drug interruption, participants will have LFTs checked again 4 days later (+/- 1 day), and the site PI and Medical Monitor will agree to a plan for further monitoring of the findings. The LFTs in this instance can also be run locally for more rapid turnaround.

LFTs do not need to be intensively monitored when ALT and AST are ≤ 3 X ULN with no elevation of bilirubin, however the investigator and the Medical Monitor will formulate a plan for serial testing of LFTs. Cessation of dosing is not required in this circumstance but may be temporarily interrupted at the discretion of the investigator.

NUMBER OF PARTICIPANTS:

Up to approximately 144 participants randomized in a 1:1:1 ratio to 100 mg/day, 300 mg/day or placebo. Additional participants may be added to replace participants with significant disruption to their visit schedule due to COVID or if there are unanticipated dropouts.

TARGET POPULATION:

INCLUSION CRITERIA:

Subjects may be included in the study only if they meet all the following criteria:

1) Men, and women of non-childbearing potential, 50-85 years of age inclusively, with a diagnosis of mild to moderate Alzheimer's disease according to the 2011 NIA-AA

criteria and at least a 6 month decline in cognitive function documented in the medical record.

- i) Non-childbearing potential for women is defined as postmenopausal (last natural menses greater than 24 months) or undergone a documented bilateral tubal ligation or hysterectomy. If last natural menses less than 24 months, a serum FSH value confirming post-menopausal status can be employed.
- ii) Male subjects who are sexually active with a woman of child-bearing potential must agree to use condoms during the trial and for 3 months after last dose unless the woman is using an acceptable means of birth control. Acceptable forms of birth control include birth control pills, or any double combination of: intrauterine device (IUD), diaphragm, sponge, and cervical cap. Periodic abstinence, coitus interruptus, exclusive use of spermicides and lactational amenorrhea method (LAM) are not acceptable contraceptive methods.
- 2) Diagnostic confirmation by amyloid PET with florbetaben or another approved amyloid PET ligand. Previous amyloid imaging study with a positive result will be accepted. If none is available, then amyloid PET will be conducted during screening. Diagnostic confirmation by a CSF sample collected at the optional screening visit lumbar puncture in place of amyloid PET will also be acceptable. Inclusion via CSF samples requires: low Aβ 42 OR low Aβ 42/40 ratio AND either increased total-tau OR increased phospho-tau based on the ranges established by the central lab.
- 3) Neuroimaging (MRI, or CT scan due to contraindication of MRI is approved by Medical Monitor) obtained during screening consistent with the clinical diagnosis of Alzheimer's disease and without findings of significant exclusionary abnormalities (see exclusion criteria, number 4). An historical MRI (or CT scan), up to 1 year prior to screening, may be used if there is no history of intervening neurologic disease or clinical events (such as a stroke, head trauma etc.) and the subject is without clinical symptoms or signs suggestive of such intervening events.
- 4) MMSE 18-26 inclusive.
- 5) No active depression and a GDS ≤6 (see exclusion criteria number 6). Subjects with a GDS >6 may be allowed to enroll if the investigator does not believe the subject is

clinically depressed. Investigators must contact the Medical Monitor to discuss eligibility.

- 6) Modified Hachinski ≤ 4.
- 7) Formal education of eight or more years.
- 8) Participants must have a caregiver/ study partner who in the opinion of the site principal investigator, has contact with the study subject for a sufficient number of hours per week to provide informative responses on the protocol assessments, oversee the administration of study drug, and is willing and able to participate in all clinic visits and some study assessments. The caregiver/ study partner must provide written informed consent to participate in the study.
- 9) Participants living at home or in the community (assisted living acceptable).
- 10) Ability to swallow CT1812 capsules.
- 11) Stable pharmacological treatment of any other chronic conditions for at least 30 days prior to screening.
- 12) Participants must be capable of providing written informed consent to the study procedures and for use of protected health information [Health Insurance Portability and Accountability Act (HIPAA) and European General Data Protection Regulation (GDPR), if applicable]. Written informed consent also shall be obtained from the responsible caregiver. All consent processes must be undertaken in the presence of a witness and prior to any study procedures.
- 13) Must consent to apolipoprotein E (ApoE) genotyping for data analysis stratification.
- 14) Participants shall be generally healthy with mobility (ambulatory or ambulatory-aided, i.e., walker or cane), vision and hearing (hearing aid permissible) sufficient for compliance with testing procedures.
- 15) Must be able to complete all screening evaluations.

EXCLUSION CRITERIA:

Participants will be excluded from the study if any of the following conditions apply:

1) Hospitalization (except for planned procedures) or change of chronic concomitant medication within one month prior to screening.

- 2) Participants living in a continuous care nursing facility.
- 3) Contraindication to the MRI examination for any reason. CT scan may be substituted for an MRI if a subject is unable to tolerate an MRI or an MRI is contraindicated for medical reasons. The proposed CT scan will be approved by the Medical Monitor on a case-by-case basis.
- 4) Screening MRI (or historical MRI, or CT scan due to contraindication of MRI if approved by medical monitor) of the brain indicative of significant abnormality, including, but not limited to, prior hemorrhage or infarct > 1 cm³, >3 lacunar infarcts, cerebral contusion, encephalomalacia, aneurysm, vascular malformation, subdural hematoma, hydrocephalus, space-occupying lesion (e.g. abscess or brain tumor such as meningioma). If a small incidental meningioma is observed, the Medical Monitor may be contacted to discuss eligibility.
- 5) Clinical or laboratory findings consistent with:
 - a. Other primary degenerative dementias such as dementia with Lewy bodies, frontotemporal dementia, Huntington's disease, Creutzfeldt-Jakob Disease, Down syndrome, etc.
 - b. Other neurodegenerative condition (Parkinson's disease, amyotrophic lateral sclerosis, etc.).
 - c. Seizure disorder.
 - d. Other infectious, metabolic or systemic diseases affecting the central nervous system (syphilis, present hypothyroidism, present vitamin B12 or foliate deficiency, other laboratory values etc.).
- 6) A current DSM-V diagnosis of active major depression, schizophrenia or bipolar disorder. Subjects with depressive symptoms successfully managed by a stable dose of an antidepressant or antipsychotic would be allowed to enroll.
- 7) Clinically significant, advanced or unstable disease that may interfere with outcome evaluations, such as:
 - a. Chronic liver disease, liver function test abnormalities or other signs of hepatic insufficiency (ALT, AST, alkaline phosphatase > 1.5 ULN, lactate dehydrogenase (LDH) > 1.5 x ULN).

- b. Respiratory insufficiency.
- c. Renal insufficiency eGFR < 50 mL/min based on the CKD-EPI formula, as calculated by the central laboratory.
- d. Heart disease (myocardial infarction, unstable angina, heart failure, cardiomyopathy within six months before screening).
- e. Bradycardia (<50 beats/min.) or tachycardia (>100 beats/min.). If the heart rate is below 50 beats/min the subject may be eligible to enroll if the Investigator has determined that the heart rate < 50 beats/min is stable and not clinically significant. If the heart rate is above 100 beats/min, the heart rate assessment may be repeated to assess eligibility.
- f. Poorly managed hypertension (systolic >160 mm Hg and/or diastolic >95 mm Hg) or hypotension (systolic <90 mm Hg and/or diastolic <60 mm Hg).
- g. Uncontrolled diabetes defined by HbA1c >7.5% in participants with diabetes. Only those subjects with known diabetes are required to get a HbA1c at screen.
- 8) History of cancer within 3 years of screening with the exception of fully excised non-melanoma skin cancers or non-metastatic prostate cancer that has been stable for at least 6 months.
- 9) Seropositive for human immunodeficiency virus (HIV).
- 10) History of acute/chronic hepatitis B or C and/or carriers of hepatitis B (seropositive for hepatitis B surface antigen [HbsAg] or anti-hepatitis C [HCV] antibody). Subjects who have evidence of resolved Hepatitis C infection (HCV RNA negative) may be considered following discussion with the Medical Monitor.
- 11) Clinically significant abnormalities in screening laboratory tests, including:
 - a. Hematocrit less than 35% for males and less than 32% for females, absolute neutrophil cell count < 1500/uL (with the exception of a documented history of a chronic benign neutropenia), absolute lymphocyte count <900/ul or platelet cell count of < 120,000/uL; INR >1.4 or other coagulopathy, confirmed by repeat assessment of:
 - i. Hematocrit

- ii. Neutrophil count
- iii. Lymphocyte count
- iv. Platelet count
 - v. PT/INR
- 12) Disability that may prevent the subject from completing all study requirements (e.g. blindness, deafness, severe language difficulty, etc.).
- 13) Within 4 weeks of screening visit or during the course of the study, concurrent treatment with antipsychotic agents, antiepileptics, centrally active antihypertensive drugs (e.g., clonidine, l-methyl dopa, guanidine, guanfacine, etc.), sedatives, opioids, mood stabilizers (e.g., valproate, lithium); or benzodiazepines, with the following exceptions:
 - a) Low dose lorazepam may be used for sedation prior to MRI scan for those participants requiring sedation. At the discretion of the investigator,
 0.5 to 1 mg may be given orally prior to the scan with a single repeat dose given if the first dose is ineffective. No more than a total of 2 mg lorazepam may be used for the MRI scan.
 - b) Stable use of eszopiclone or zolpidem for sleep is allowed. Stable use of short-acting benzodiazepines and trazadone specifically as sleep aids are allowed.
- 14) Any disorder that could interfere with the absorption, distribution, metabolism or excretion of drugs (e.g. small bowel disease, Crohn's disease, celiac disease, or liver disease).
- 15) Nootropic drugs except stable AD meds (acetylcholinesterase inhibitors or memantine).
- 16) Suspected or known drug or alcohol abuse, i.e. more than approximately 60 g alcohol (approximately 1 liter of beer or 0.5 liter of wine) per day indicated by elevated MCV significantly above normal value at screening.
- 17) Suspected or known allergy to any components of the study treatments.
- 18) Enrollment in another investigational study or intake of investigational drug within the previous 30 days or five half-lives of the investigational drug, whichever is longer.

- 19) Intake of drugs or substances potentially involved in clinically significant induction or inhibition of CYP3A4 or P-gp mediated drug interactions with CT1812, within 4 weeks or five half-lives of the interacting drug prior to administration of CT1812 and throughout the course of the study. Grapefruit juice should be avoided in the two weeks prior to dosing and throughout the course of the study. See Appendix A for a complete list of prohibited substances. See Section 9.3.1 for handling of Paxlovid ™ administration for COVID infection during the study.
- 20) Any prior exposure to immunomodulators, anti Aβ vaccines, or passive Aβ immunotherapies for AD (e.g. monoclonal antibodies) and/or exposure to BACE inhibitors within the past 30 days.
- 21) Any vaccination within one week of the baseline visit.
- 22) Any condition, which in the opinion of the investigator or the sponsor makes the participant unsuitable for inclusion.

LENGTH OF STUDY:

Each participant and caregiver will participate in a screening period of up to 42 days, followed by a double-blind treatment period of 182 (+/- 7) days and a follow up visit at Day 210 for a total of 254 days of study participation.

DOSAGE, DOSE FORM, AND ROUTE OF ADMINISTRATION:

CT1812, 100 mg or 300 mg

Study Drug will be capsules of identical appearance containing either placebo or CT1812 fumarate.

Study drug will be taken by mouth once each morning with or without food.

EVALUATION CRITERIA:

A DSMB (Data and Safety and Monitoring Board) will oversee the safety of the trial. This committee will include three independent experts, including an independent statistician. Safety data will be provided to the DSMB at quarterly intervals during the trial. The study clinician and study Medical Monitor will review trial safety data biweekly and more frequently as the rate of enrollment and safety data warrant. Similarly, more frequent ad

hoc meetings of the DSMB will occur if ongoing safety data indicate interim meetings are indicated.

The DSMB will review the safety and tolerability of CT1812 of the participant enrolled in the study. They may also recommend additional safety and/or monitoring measures.

Safety and Tolerability Measures:

- Adverse events.
- Serious Adverse Events.
- Physical and neurological examinations.
- Vital signs body temperature, systolic and diastolic blood pressure, pulse rate and respiration rate.
- Electrocardiogram (ECG).
- Clinical laboratory tests: hematology, biochemistry, coagulation, serology and urinalysis.
- Columbia Suicide Severity Rating Scale (C-SSRS).

Efficacy Measures:

- Mini Mental State Exam (MMSE).
- ADAS-cog 11 and ADAS-cog 13 (Delayed Recall and digit cancellation added to ADAS-11 in the ADAS-13).
- Neuropsychological Test Battery (NTB). NTB includes Trails A & B, Digit Span,
 Letter & Category Fluency (COWAT and CFT).
- ADCS-Clinical Global Impression of Change (CGIC).
- ADCS-Activities of Daily Living (ADCS-ADL).

Exploratory Measures:

- Pharmacokinetic: Plasma and CSF CT1812.
- Pharmacodynamic: CSF- Aβ, tau, phospho-tau, Neuro Filament Light Chain (NFL), neurogranin, synaptotagmin, SNAP25 (synaptosomal-associated protein 25) and

 $A\beta$ oligomers. Other exploratory target engagement biomarkers may also be evaluated.

STATISTICAL METHODS:

Analysis Populations

The safety population will include all participants receiving one or more doses of study treatment. Individual data for all enrolled participants will be presented in data listings, sorted by participant and dosing arm.

An interim analysis will be performed once the first 24 participants have completed six months of dosing. Details of the interim analysis can be found in the statistical analysis plan.

Study Sample Size

Groups of up to 48 participants per dose level are felt to give adequate sensitivity to detect adverse events. A sample size of 48 participants for each dose level (100 mg, 300 mg) has 91% power to detect at least 1 occurrence of any drug-related AE with a true prevalence in the treated population of 5%.

Additional participants may be added to replace participants with significant disruption to their visit schedule due to COVID or if there are unanticipated dropouts.

Additionally, for the primary exploratory efficacy analysis relating to the ADAS-COG 11 comparing the combined CT1812 treatment groups versus the placebo group, 48 participants per group provides 81% power to show a treatment difference of 3.0 points assuming a two-sided test at the alpha=0.05 level of significance, assuming a SD of 5.4 points, and a dropout rate of 15%.

Data Analysis

All descriptive statistical analyses will be performed using the current version of SAS statistical software, unless otherwise noted.

Adverse Events will be assessed by the investigator for severity and will be coded for summarization using the current version of Medical Dictionary for Regulatory Activities (MedDRA[®]). Adverse Events will be summarized by Preferred Term and System Organ

Class, for each dose group (including placebo).

Laboratory measures will be summarized by treatment group and time-point both as absolute values and as change from baseline, with descriptive statistics summarizing each group and time point. Similar presentation will be used for vital signs and for ECG interval measurements, and changes from pre-treatment baseline.

Concomitant medications will be coded using the current version of WHO Drug Dictionary or Concomitant medications will be summarized and listed.

Efficacy endpoints will be summarized by treatment group and time-point using descriptive statistics as both absolute values and as change from baseline. Differences between treatment groups will be assessed using a mixed model for repeated measures (MMRM). The difference between each treatment group and the placebo at each time-point will be estimated based on the least square means (LSM) from the MMRM. Exploratory analyses of potential pharmacodynamics markers in CSF and plasma will be conducted using appropriate statistical tests.

Additional statistical details will be provided in a prospective statistical plan.

Contents

1	Stud	y Organizational Structure	4
2	Proto	ocol Synopsis	5

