9.5 Participant Withdrawal Procedures

9.5.1 Follow-up Procedures for Participants Who Withdraw Prematurely

The date and the reason for study drug discontinuation or participant withdrawal from the study must be recorded on the Case Report Form. If the participant has received one or more doses of clinical trial material, and has not withdrawn consent, the participant shall return for the End of Study (EOS) visit. The EOS visit for early terminations will occur within 2 weeks of the last dose.

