#### 4.1. Introduction

Data processing, tabulation of descriptive statistics, calculation of inferential statistics, and graphical representations will be performed primarily using SAS (release 9.4 or higher). If the use of other software is warranted, the final statistical methodology report will detail what software was used for what purposes.

Continuous (quantitative) variable summaries will include the number of participants (n) with non-missing values, mean, standard deviation (SD), median, minimum, and maximum. Other statistics such as coefficient of variation (%CV), quartiles, confidence intervals (CIs), and number of missing values may be added as appropriate.

Categorical (qualitative) variable summaries will include the frequency and percentage of participants who are in the particular category or each possible value. In general, the denominator for the percentage calculation will be based upon the total number of participants in the study population within each treatment group, unless otherwise specified. The denominator for by-visit displays will be the number of participants in the relevant study population with non-missing data at each visit.

The minimum and maximum will be reported with the same degree of precision (i.e., the same number of decimal places) as the observed data. Measures of location (mean and median) will be reported to 1 degree of precision more than the observed data. Measures of spread (SD) will be reported to 2 degrees of precision more than the observed data.

Percentages will be presented to 1 decimal place, unless otherwise specified.

Unless otherwise indicated, all statistical tests will be conducted at the 0.05 significance level using 2-tailed tests, and P-values will be reported. A P-value of  $\leq$ 0.10 but >0.05 will be considered evidence of a trend. Corresponding 95% CIs will be presented for statistical tests.

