#### 5. Analysis Populations

The following analysis populations are planned for this study:

- All Subjects: The All Subjects population includes all participants who sign the ICF and get screened for the study.
- Safety Population (SAF): The Safety Population includes all participants who receive one or more doses of study medication.
- Efficacy Modified Intent-To-Treat Population (mITT): The Efficacy mITT Population includes all randomized participants who receive any amount of study drug and who have a baseline and at least one post-baseline assessment of the ADAS-Cog 11 total score.
- Completers Population (CP): The Completers Population includes all randomized participants who completed the study (i.e., who did not prematurely withdraw). There is no expectation that a participant included in the CP will have attended every single scheduled visit; as long as the participant completed the study, they will be included in the population.
- **Pharmacokinetic Population (PK):** The Pharmacokinetic Population includes all participants in the SAF who had at least one quantifiable concentration of CT1812.

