#### 7.4. Exposure and Compliance

For all of the below formulas, i = individual participant for the entire treatment period.

• Total days of exposure will be calculated as:

$$\sum_{i}$$
 Days on Study Drug

• Study drug compliance will be calculated as:

$$\frac{\sum_{i} Actual \ Capsules \ Taken}{\sum_{i} Planned \ Capsules} \times 100$$

Compliance will be calculated using drug accountability data over the entire treatment period for each participant, up to treatment completion or discontinuation. Planned capsules will be calculated as 2 × the number of days between the first and last dose of study drug (inclusive).

Study drug exposure and compliance information will also be listed.

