#### 9.1. Adverse Events

Treatment-emergent AEs will be summarized in all AE tables. A TEAE is defined as any AE with an onset date/time on or after the first dose of study drug. All AE summary tables will include the number and percentage of participants with an AE within a category, system organ class (SOC), or preferred term (PT).

An overall summary of the number and percentage of participants with TEAEs will be provided by treatment group. Frequencies and percentages of the following will be included: with any TEAE, participants with any TEAE related to treatment, participants with any TEAE leading to

treatment discontinuation, participants with any serious treatment emergent AE (SAE), participants with any SAE related to treatment, and participants with any TEAE leading to death.

The incidence of TEAEs will be summarized with frequencies and percentages by the following:

- PT in descending order of frequency
- SOC and PT
- SOC, PT, and maximum severity (Mild; Moderate; Severe)
- SOC, PT, and maximum relationship to study drug (Not Related; Related)

Incidences other than the PT summary will be presented alphabetically by SOC and PT. Participants with multiple events within the same SOC and PT will be counted once per SOC and PT. TEAEs with a missing severity will be considered severe and TEAEs with a missing relationship to study drug will be considered related. AEs with a relationship of study drug of possibly or probably related will be considered related.

All AEs will be presented in a listing. AEs that are treatment emergent will be flagged.

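### AE incidence is reported only as a percentage of everyone dosed; if early stopping differs between arms, events that accrue over time can be diluted, and a time-at-risk summary would show it cheaply

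*Protocol*

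**What the plan says.** Safety and tolerability is the primary objective in both documents (Protocol 5.1, SAP 2.1.1). The synopsis, under Data Analysis, fixes only the grouping: "Adverse Events will be summarized by Preferred Term and System Organ" Class, by dose group. Protocol 15.4 adds that incidence will be compared, without naming a method.

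The statistic itself is in the SAP:

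- **Statistic (9.1):** "All AE summary tables will include the number and percentage of participants with an AE within a category", system organ class or preferred term.
- **Denominator (4.1), as the general rule:** "the denominator for the percentage calculation will be based upon the total number of participants in the study population within each treatment group".
- **Population (5):** "The Safety Population includes all participants who receive one or more doses of study medication".

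Time under observation differs by completion status:

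- **Completers** are treated for 182 days and seen again at Day 210 (Protocol synopsis, Length of Study).
- **Early stoppers:** "The EOS visit for early terminations will occur within 2 weeks of the last dose" (Protocol 9.5.1). Protocol 13.2.3 also asks them to report AEs for 30 days after withdrawal.
- **Some safety stops end participation.** The synopsis withdraws a participant from the study when a qualifying liver-test elevation has no alternative explanation.

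SAP 7.4 derives exposure ("Total days of exposure will be calculated as" a sum of days on study drug), but no AE table uses it. Neither document plans a person-time rate or a time-to-first-event analysis for AEs. The end of the TEAE window also differs: Protocol 13.2.1 closes it at the last dose, and SAP 9.1 leaves it open.

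**The concern.** A percentage of everyone dosed treats a participant watched for 10 weeks like one watched for 30. For an event that keeps arising during treatment, the shorter observation gives fewer chances to record it. If one CT1812 arm, or the pooled group, loses more participants early than placebo, its percentage for such an event falls for reasons unrelated to the drug's effect on that event. A real excess could then be understated on the primary objective.

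Unequal stopping is plausible but not predicted by the documents. Protocol 4.3 reports that in the 28-day study in Alzheimer's disease total AEs became more frequent with dose. Some of those AEs were more frequent at 560 mg, a dose above those used here.

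**Working it through.** **1. The plan's own safety figure.** With 48 participants per dose and a true AE prevalence of 5%, the chance of at least one occurrence is 1 − 0.95^48 = 0.915. The stated 91% reproduces. It takes all 48 as fully observed. If 5% is the risk over full follow-up and 15% stop at times spread evenly over Days 0–182, the chance becomes 89.5–90.0%, depending on whether AE capture ends 0 to 30 days after the last dose. The detection argument is barely affected. The between-arm comparison is the issue.

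**2. Inputs for the comparison.**
- From the documents: a completer is observed for 210 days = 30 weeks. An early stopper's last visit is up to 2 weeks after the last dose. Overall dropout is 15%, stated only for the efficacy power.
- Assumed, because the documents give no figure: 26-week event risk of 20% at a constant rate; stopping at week 8, so last contact at week 10; stopping fractions d by arm; stopping unrelated to the event.

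**3. Formula.** h = −ln(0.8)/26 = 0.00858 per week.
- Completer risk = 1 − exp(−30h) = 22.7%.
- Stopper risk = 1 − exp(−10h) = 8.2%.
- Arm percentage = (1 − d) × 22.7% + d × 8.2%.

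**4. Results with no drug effect.**

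| Stopping, CT1812 vs placebo | Table shows | Ratio |
|---|---|---|
| 30% vs 10% | 18.4% vs 21.3% | 0.86 |
| 25% vs 10% | – | 0.90 |
| 17.5% vs 10% | 20.2% vs 21.3% | 0.95 |
| Equal in both arms | same percentage | 1.00 |

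The 17.5%/10% split is the one that fits the planned dropout: (17.5 + 17.5 + 10)/3 = 15%. The 30%/10% split gives (30 + 30 + 10)/3 = 23%.

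With a true 1.2-fold rate on CT1812 and 30% vs 10% stopping, completer risk is 26.6% and stopper risk 9.8%. The arm shows 0.7 × 26.6% + 0.3 × 9.8% = 21.5% against 21.3%.

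**5. Sensitivity of the 0.86.**
- Crediting stoppers with the full 30-day reporting period: 0.88.
- Stopping spread evenly over treatment: 0.90 with 14-day capture, 0.92 with 30-day capture.
- Both changes with 17.5% vs 10% stopping: 0.97.

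**6. Where it vanishes or reverses.** These cases use 5% vs 30% stopping spread evenly.
- *Early-onset events* (assumed mean onset 14 days, true risk 20%): the arms differ by 0.4 points or less.
- *Any TEAE when AEs cause stopping*: arm percentage = (1 − d) × risk + d × [q + (1 − q) × m], where q is the share of stoppers who stopped because of a TEAE and m is the risk among the other stoppers. With 210-day risk 20%, 14-day capture, m = 10.4% and q = 0.5, the table shows 21.8% vs 30.6%. The arm with more stopping now looks worse, because each such stopper is already in the numerator.

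**7. The obvious remedy has its own weakness.** Take 30% vs 10% stopping as in step 4, but let 20% of each arm have the event at week 2.
- The crude percentages are both 20%, which is correct.
- Weeks at risk per participant are 0.2 × 2 + 0.8 × (0.7 × 30 + 0.3 × 10) = 19.6, against 0.2 × 2 + 0.8 × (0.9 × 30 + 0.1 × 10) = 22.8.
- The rates are 53 and 46 per 100 participant-years, a spurious ratio of 22.8/19.6 = 1.16.

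A person-time rate alone is therefore not enough.

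**The case against.** The strongest reply is that unequal stopping will already be visible. SAP 7.1 tabulates premature discontinuation with reasons by arm. SAP 9.1 and 9.1.1 tabulate TEAEs leading to discontinuation, all AEs are listed, and by-visit safety summaries use only participants with data at that visit. This stands in part: those tables would alert a reader, but they do not correct an AE percentage for lost time at risk.

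Second, the effect is small against the trial's precision. At 20% incidence the standard error of a 96-against-48 difference is √[0.16 × (1/96 + 1/48)] = 7.1 points, so even the 2.9-point shift at 30% vs 10% is under half a standard error. The SAP specifies no AE test. This stands, and it limits the priority of the point.

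Third, every driver of the size (stopping by arm, its timing, event rates) is assumed. This also stands. A reader might infer that an arm with more early stopping will look safer, or that poor tolerability hides AE risk. The documents do not support that as a general statement. It requires unequal stopping, events that accrue over time, and stopping largely unrelated to AEs. When poor tolerability is itself the reason for stopping, the event is counted and the sign can reverse.

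**Conclusion.** The point holds in conditional form, as a cheap improvement and not a flaw that undermines the safety analysis. The plan reports AE incidence only as a percentage of everyone dosed, early stoppers are watched for much less time, and nothing planned accounts for that.

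For events that accrue over time, the no-effect ratio is about 0.95 to 0.97 if stopping matches the planned 15% overall with a modest imbalance. It reaches 0.86 only under the more extreme assumption of 30% vs 10% stopping at week 8. That the direction depends on why and when people stop is itself a reason not to rely on the crude percentages alone.

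**What to change.** In SAP 9.1, keep the crude percentages and add beside them, for placebo, 100 mg, 300 mg and pooled CT1812:

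- (a) mean AE observation time per arm;
- (b) participants with a first event per 100 participant-years, counted from first dose to the first event or last AE contact;
- (c) time-to-first-event cumulative incidence at Day 182, which does not assume a constant rate.

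Produce (b) and (c) for any TEAE, related TEAEs, SAEs and preferred terms reported in at least 5% of any arm. Reconcile the end of the TEAE window between Protocol 13.2.1 and SAP 9.1 first, since observation time is undefined until one end date is stated.

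The cost is a little more programming from dates already collected, with no change to sample size, alpha or conduct. Item (b) can mislead for front-loaded events, so it should not stand without (c). Item (c) still assumes that participants who leave have the same later risk as those who stay. All of it remains descriptive at this sample size.
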